#### **6.3.2.2. Derivation Rules**

##### **Derived Laboratory Tests**

Not applicable.

##### **Fasted and Non-Fasted Results**

Laboratory tests that are sensitive to the fasting status: glucose, triglycerides, and insulin.

For these laboratory tests, only results from blood samples drawn in a fasted state will be included in the analysis. Results from blood samples taken in a non-fasted (not fasting and fasting not declared) state will be listed only and no toxicities or abnormalities will be calculated. Laboratory results for which the fasting status is missing will be considered as taken non-fasted.

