#### **4.5.3. Calculation of Percentages**

Frequencies and percentages will be generated for categorical parameters.

For event-type data (e.g. adverse events), the denominator will be all subjects in the analysis set and analysis period. For other data (e.g. worst-case analysis of assessments), the denominator will be all subjects with (post-baseline) data for the parameter, in the analysis set and analysis window/period.

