### **6.3.2. Laboratory Safety**

#### **6.3.2.1. Available Data**

Laboratory tests scheduled are described in the protocol section 8.5.2. In addition, the derived laboratory tests described in Section [6.3.2.2](#) will be added.

The statistical analyses will only present results in Standard International (SI) standardized units. Other units will not be presented.

Only data provided by the central laboratory will be used in tables and figures. Results from local labs will be listed only.

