#### **6.3.2.7. Worst-Case Principle**

##### **Toxicity Grading**

The worst-case post-baseline toxicity grade 0, 1, 2, 3 or 4 will be determined per subject, per laboratory test (and direction, increases and decreases) and for each analysis period, using all non-missing post-baseline records (including unscheduled and FU visits).

The worst-case toxicity grade is the highest toxicity grade corresponding to the highest laboratory test value (by direction, increases and decreases). In case of several equal highest post-baseline actual values, the earliest occurrence will be taken for the analyses and will be flagged in the listings.

- Grade 0: all post-baseline toxicity grades are classified as 0
- Grade 1: all post-baseline toxicity grades are classified as  $\leq 1$
- Grade 2: all post-baseline toxicity grades are classified as  $\leq 2$
- Grade 3: all post-baseline toxicity grades are classified as  $\leq 3$
- Grade 4: all post-baseline toxicity grades are classified as  $\leq 4$

If any record is missing, then the toxicity grade is considered as 'missing'.

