## APPENDIX

### Appendix I: Laboratory: Toxicity Grading

The following tables contain a list of safety tests with associated gradings. There may be tests in this table that are not measured in this particular study.

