**Table 7 Gradings for Blood Chemistry Parameters**

Parameter	L1	L2	L3	L4	H1	H2	H3	H4
Alanine aminotransferase (ALT)	NA	NA	NA	NA	>ULN	>3.0 x ULN	>5.0 x ULN	>8.0 x ULN
Aspartate aminotransferase (AST)	NA	NA	NA	NA	>ULN	>3.0 x ULN	>5.0 x ULN	>8.0 x ULN
Gamma-glutamyl transferase (GGT)	NA	NA	NA	NA	>ULN	>2.5 x ULN	>5.0 x ULN	>20.0 x ULN
Alkaline Phosphatase (total)	NA	NA	NA	NA	>ULN	>2.5 x ULN	>5.0 x ULN	>20.0 x ULN
Lactate dehydrogenase (LDH)	NA	NA	NA	NA	>ULN	NA	NA	NA
Total bilirubin	NA	NA	NA	NA	>ULN	>1.5 x ULN	>3.0 x ULN	>10.0 x ULN
Amylase	NA	NA	NA	NA	>ULN	>1.5 x ULN	>2.0 x ULN	>5.0 x ULN
Lipase	NA	NA	NA	NA	>ULN	>1.5 x ULN	>2.0 x ULN	>5.0 x ULN
Total protein	<LLN	<5.5 g/dL	<5.0 g/dL	NA	NA	NA	NA	NA
C-reactive protein (CRP)	NA	NA	NA	NA	>5mg/L	>10mg/L	>20mg/L	>30mg/L
Activated partial thromboplastin time (APTT)	NA	NA	NA	NA	>ULN	>1.5 x ULN	>2.5 x ULN	NA
Prothrombin time (PT)	NA	NA	NA	NA	≥1.10 x ULN	≥1.25 x ULN	≥1.50 x ULN	≥3.00 x ULN

Parameter	L1	L2	L3	L4	H1	H2	H3	H4
International normalized ratio (INR)	NA	NA	NA	NA	>1.2 x Baseline	>1.5 x Baseline	>2.5 x Baseline	NA
Creatinine	NA	NA	NA	NA	>ULN	>1.5 x ULN	>3.0 x ULN	>6.0 x ULN
Glucose ( fasting )	<LLN	<55 mg/dL; <3.0 mmol/L	<40 mg/dL; <2.2 mmol/L	<30 mg/dL; <1.7 mmol/L	>ULN	>125 mg/dL; ≥6.95 mmol/L	>250 mg/dL; ≥13.89 mmol/L	≥500 mg/dL; ≥27.75 mmol/L
Glucose ( non-fasting )	<LLN	<55 mg/dL; <3.0 mmol/L	<40 mg/dL; <2.2 mmol/L	<30 mg/dL; <1.7 mmol/L	>ULN	>160 mg/dL; ≥8.89 mmol/L	>250 mg/dL; ≥13.89 mmol/L	≥500 mg/dL; ≥27.75 mmol/L
HbA1c	NA	NA	NA	NA	> 6.0 %	> 6.5 %	NA	NA
Fasting insulin	<2.6 µU/mL or 18.1 pmol/L	NA	NA	NA	>24.9 µU/m or 172.9 pmol/L	NA	NA	NA
Cholesterol	NA	NA	NA	NA	>ULN	>300 mg/dL; ≥7.75 mmol/L	>400 mg/dL; ≥10.34 mmol/L	>500 mg/dL; ≥12.92 mmol/L
Low-density lipoprotein (LDL)	NA	NA	NA	NA	>ULN	≥160 mg/dL; ≥4.12 mmol/L	≥190 mg/dL; ≥4.90 mmol/L	NA
High-density lipoprotein (HDL)	<LLN	<40 mg/dL; <1 mmol/L	NA	NA	NA	NA	NA	NA

Parameter	L1	L2	L3	L4	H1	H2	H3	H4
Triglycerides	NA	NA	NA	NA	>ULN	>300 mg/dL; >3.42 mmol/L	>500 mg/dL; >5.7 mmol/L	>1,000 mg/dL; >11.4 mmol/L
Calcium (corrected for albumin)	<LLN	<8.0 mg/dL; <2.0 mmol/L	<7.0 mg/dL; <1.75 mmol/L	<6.0 mg/dL; <1.5 mmol/L	>ULN	>11.5 mg/dL; ; >2.9 mmol/L	>12.5 mg/dL; ; >3.1 mmol/L	>13.5 mg/dL; ; >3.4 mmol/L
Ionized calcium	<LLN	<1.0 mmol/L	<0.9 mmol/L	<0.8 mmol/L	>ULN	>1.5 mmol/L	>1.6 mmol/L	>1.8 mmol/L

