**Table 8 Gradings for Urine Analysis Parameters**

Parameter	L1	L2	L3	L4	H1	H2	H3	H4
Urine erythrocytes	NA	NA	NA	NA	≥ULN	≥10 cells/HPF	NA	NA
Urine protein	NA	NA	NA	NA	1+ proteinuria	2+ and 3+ proteinuria; urinary protein <3.5 g/24 hrs	urinary protein ≥3.5 g/24 hrs; 4+ proteinuria	NA
Urine glucose	NA	NA	NA	NA	>ULN (presence of glucose)	NA	NA	NA

LLN: lower limit of normal, ULN: upper limit of normal, NA: not applicable.

Any laboratory parameter with treatment-emergent (i.e., worsening from baseline) abnormalities of grade 2 or above (ie, H2/L2 or higher/lower) should be considered a 'marked laboratory abnormality'. Marked laboratory abnormalities should be described in a corresponding section of the CSR as per ICH E3 guidance, section 12.4.2.3.

**Appendix II: Vital Signs and Electrocardiogram grading****Table 9 Gradings for Vital Signs and Electrocardiogram Parameters**

Parameter	L1	L2	L3	L4	H1	H2	H3	H4
Systolic blood pressure (mmHg)	<90	<60	NA	NA	NA	≥140	≥160	≥180
Diastolic blood pressure (mmHg)	<60	<45	NA	NA	NA	≥90	≥100	≥120
Heart rate (bpm)	<60	<50	<40	NA	>100	>115	>130	NA
Body temperature (°C)	NA	<35	NA	NA	>38	NA	NA	NA
Respiratory rate (breaths per minute)	<12	NA	NA	NA	>20	NA	NA	NA
O 2 saturation (%)	<95	<90	NA	NA	NA	NA	NA	NA
Weight	≥7% decrease from baseline	NA	NA	NA	≥7% increase from baseline	NA	NA	NA
QTc interval on ECG (ms)	NA	NA	NA	NA	>450	>480	>500	NA
QTc change from baseline (ms)	NA	NA	NA	NA	NA	>30	>60	NA
PR interval on ECG (ms)	<110	NA	NA	NA	>200	NA	NA	NA
QRS complex on ECG (ms)	<60	NA	NA	NA	>120	NA	NA	NA

Source: FRM-MED-005/006, valid on 08JUL2020.

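### SAP 6.3.2.2 gives no toxicity grade to glucose that is non-fasted or of unknown fasting status, although the schedule draws glucose at visits without required fasting and Table 7 already has a non-fasting row (minor)

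*SAP*

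**What the plan says.** SAP 6.3.2.2 names glucose, triglycerides and insulin as fasting-sensitive and analyses only samples drawn fasted. Results "taken in a non-fasted (not fasting and fasting not declared) state will be listed only and no toxicities or abnormalities will be calculated". It adds: "Laboratory results for which the fasting status is missing will be considered as taken non-fasted".

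Other parts of the plan bear on this:

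- Protocol 6.3.3 and 8.1 require fasting at Visits 1, 4 and 5. Protocol 8.11 schedules safety chemistry at every visit, including ED and FU, and its footnote 7 limits fasted glucose to Visits 1, 4 and 5. Protocol 8.5.2 lists glucose and fasted glucose as separate tests.
- SAP 6.3.2.7 derives the worst-case grade "using all non-missing post-baseline records (including unscheduled and FU visits".
- SAP Appendix I, Table 7, has separate fasting and non-fasting glucose rows. The non-fasting H2 cell reads ">160 mg/dL; ≥8.89 mmol/L". The appendix opens with a caveat: "There may be tests in this table that are not measured in this particular study".
- The note after Table 8 says that "treatment-emergent (i.e., worsening from baseline) abnormalities of grade 2 or above (ie, H2/L2 or higher/lower) should be considered a" marked laboratory abnormality, to be described in the study report.
- SAP 6.3.2.9 lists both glucose and fasted glucose for descriptive summary without saying how they differ.

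**The concern.** Restricting means and changes from baseline to fasted samples is sensible. Refusing any grade to the remaining samples is a different step. A severe low or high glucose matters whether or not the subject has eaten, and the SAP's own thresholds for Grades 3 and 4 do not depend on fasting state.

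Under the rule such a value is absent from the worst-case, shift, treatment-emergent and marked-abnormality outputs. SAP 4.5.3 sets the percentage base for assessments: "the denominator will be all subjects with (post-baseline) data for the parameter". Read with 6.3.2.2, a subject with no declared-fasted post-baseline sample would also leave the glucose denominator. This falls mainly on early stoppers: protocol 6.4 asks them to attend ED and FU visits, and neither requires fasting. It remains relevant after early termination because SAP section 1 retains the safety analyses.

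**Working it through.** The plan states no figure on this point, so the check is a count and a comparison of threshold rows.

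**1. Post-baseline panels with required fasting.** Inputs: chemistry visits from protocol 8.11; fasting visits from protocol 6.3.3. Visit 1 blood is predose and serves as baseline.

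| Subject's course | Post-baseline panels | Fasting required | Count |
|---|---|---|---|
| Completer | V2, V3, V4, V5, FU | V4, V5 | 2 of 5 (40%) |
| Stops between V4 and V5 | V2, V3, V4, ED, FU | V4 | 1 of 5 (20%) |
| Stops between V3 and V4 | V2, V3, ED, FU | none | 0 of 4 |
| Stops between V2 and V3 | V2, ED, FU | none | 0 of 3 |
| Stops before V2 | ED, FU | none | 0 of 2 |

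**2. From required to graded.** Grading needs fasting to be declared. A completer with no fasting status recorded has 0 of 5 graded; one who is fasted and declared so at every visit has 5 of 5. The documents do not locate the study within that range.

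**3. The two Table 7 rows.** The SI thresholds are the relevant ones: "The statistical analyses will only present results in Standard International (SI) standardized units".

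- Identical cells: L1 <LLN, L2 <3.0, L3 <2.2, L4 <1.7, H1 >ULN, H3 ≥13.89, H4 ≥27.75 mmol/L. That is 7 of 8.
- Different cell: H2, ≥6.95 (fasting) against ≥8.89 (non-fasting).
- The rows therefore disagree only from 6.95 to <8.89 mmol/L: 7.5 is H2 fasting and H1 non-fasting, while 8.89 is H2 in both.

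**4. Severe values that would go ungraded.** Table 7's unit factor is 250 / 13.89 = 18.0.

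- 35 mg/dL / 18.0 = 1.94 mmol/L, which is <2.2 but not <1.7: L3 in both rows.
- 520 mg/dL / 18.0 = 28.9 mmol/L, which is ≥27.75: H4 in both rows.

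If non-fasted, neither receives a grade under 6.3.2.2.

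**5. Denominator (assumed x).** If x of the 20 planned active subjects have no declared-fasted post-baseline glucose, the base is 20 − x: 20 for x = 0, 18 for x = 2, 15 for x = 5. The documents do not give x.

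**6. After the fix.** With the non-fasting row applied to all other samples, every scheduled panel can be graded: 5 of 5, 5 of 5, 4 of 4, 3 of 3 and 2 of 2 in the order of the table.

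**The case against.** The strongest reply is that the rule is deliberate. It is specific, so it qualifies the general worst-case wording in 6.3.2.7, and it keeps graded values comparable with a Visit 1 baseline that is required to be fasted. A reader might infer that the non-fasting row proves the SAP contradicts itself. The Appendix I caveat prevents that reading of the row taken alone. It does not make the row irrelevant, because glucose without required fasting is measured in this study.

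The loss is also unproven. Visits are in the morning (protocol 6.3.3) and dosing-day safety bloods are predose (protocol 8.1), so Visit 2 and 3 samples may well precede breakfast.

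Safeguards exist, each partial:

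- Individual values are listed.
- Grade 3 and higher laboratory alerts go to investigator and sponsor (protocol 5.5), with no scale or fasting rule stated.
- Adverse event recording is mandatory in the circumstances of protocol 11.1.5 and otherwise rests on judgement (protocol 8.5.2). Recorded events reach the graded adverse event tables.
- HbA1c is graded, but only H1 (>6.0%) and H2 (>6.5%), with no low side.
- Urine dipstick glucose is collected at every visit and tabulated by time point (SAP 6.3.2.5), without grades.
- The Safety Monitoring Committee reviews unblinded safety data (protocol 10.1).

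These lower the priority. They do not replace a graded table by treatment group.

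The comparability argument is sound for mild highs: H1 is simply above the normal limit, so a fed sample can reach it because of a meal. The fix must allow for that.

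**Conclusion.** The point holds at minor priority. A stated rule removes glucose results from graded safety outputs, including values whose grade is the same in either fasting state. Fasting is required at 2 of 5 post-baseline panels for a completer and at none for anyone stopping before Visit 4.

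Two stronger readings are tempting and unsupported. One is that a completer is assured two graded panels: declaration is also needed, so these are counts of required-fasted visits only. The other is that glucose toxicity has in fact been missed. No visible text reports a glucose signal, the study stopped for liver toxicity (SAP section 1), and the number stopping before Visit 4 is not given.

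The conclusion assumes that the glucose grading outputs were among the safety analyses retained. SAP section 1 marks provisions that no longer apply in grey, and that shading cannot be seen in the text available.

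**What to change.** - Keep descriptive statistics, L/N/H classes and the fasted-glucose tables on fasted samples only.
- Grade all other glucose, including missing status (already treated as non-fasted), with the existing Table 7 non-fasting row, as a separate labelled parameter.
- Use the last predose glucose in any fasting state as its reference baseline, and say on which row it is graded. Otherwise a subject without a non-fasted predose value has a missing baseline, and SAP 6.3.2.6 would call every Grade 1 to 4 result treatment-emergent.
- In its treatment-emergent table show L1–L4 and H2–H4 only, so that meal-driven H1 shifts are not counted. This matches keeping L/N/H fasted-only.
- Footnote that a truly fasted but undeclared value from 6.95 to <8.89 mmol/L would be under-graded as H1. No additional grade category is needed.
- State in 6.3.2.9 that *glucose* is this graded-only parameter and *fasted glucose* the one with descriptive statistics.
- State as a limitation that triglycerides fall under the same rule and stay fasted-only, since Table 7 has no non-fasting row for them.

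Cost: some SAP text and one extra table parameter, with no new data or thresholds. Some meal-related H2 results will be compared with a usually fasted baseline and may count as marked abnormalities; this should be footnoted.

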#### **6.3.2.3. Definition of Toxicity Grades**

Toxicity grades will only be derived for laboratory tests for which toxicity grades are available.

Toxicity grades will be determined as implemented in the attached table ([Appendix I](#)).

For elevations (H1 to H4), values under the threshold of H1 are reported as 'Grade 0'.

For elevations (L1 to L4), values above the threshold of L1 are reported as 'Grade 0'.

#### **6.3.2.4. Definition of Non-Graded Abnormalities**

For all laboratory tests provided by the laboratory, the position of the actual analysis values versus their normal ranges will be determined directly by using the derived position indicator, expressing the classes for these analysis values as low (L), normal (N) or high (H). L, N and H are further referred to as non-graded abnormalities.

#### **6.3.2.5. Urinalysis Tests with Categorical Results**

Results of urinalysis with qualitative results will be tabulated by time point. No toxicity grading or non-graded abnormalities will be derived.

#### **6.3.2.6. Treatment-Emergent Principle**

##### **Toxicity Grades**

A post-baseline toxicity grade 1, 2, 3 or 4 is defined as treatment-emergent when higher than the toxicity grade of the baseline result or when there is a change in direction (from H to L or from L to H). If the baseline result is missing, a post-baseline toxicity grade 1, 2, 3 or 4 will be considered as treatment-emergent.

##### **Non-graded Abnormalities**

A post-baseline non-graded abnormality class L or H is defined as treatment-emergent when it differs from the abnormality class of the baseline result. If the baseline result is missing, a post-baseline abnormality L or H will be considered as treatment-emergent.

#### **6.3.2.7. Worst-Case Principle**

##### **Toxicity Grading**

The worst-case post-baseline toxicity grade 0, 1, 2, 3 or 4 will be determined per subject, per laboratory test (and direction, increases and decreases) and for each analysis period, using all non-missing post-baseline records (including unscheduled and FU visits).

The worst-case toxicity grade is the highest toxicity grade corresponding to the highest laboratory test value (by direction, increases and decreases). In case of several equal highest post-baseline actual values, the earliest occurrence will be taken for the analyses and will be flagged in the listings.

- Grade 0: all post-baseline toxicity grades are classified as 0
- Grade 1: all post-baseline toxicity grades are classified as  $\leq 1$
- Grade 2: all post-baseline toxicity grades are classified as  $\leq 2$
- Grade 3: all post-baseline toxicity grades are classified as  $\leq 3$
- Grade 4: all post-baseline toxicity grades are classified as  $\leq 4$

If any record is missing, then the toxicity grade is considered as 'missing'.

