##### **4.4.1.2. Handling of Missing Result Data**

No imputation will be done of missing result data unless otherwise specified. That is, an observed case (OC) analysis will be performed. Endpoints analyzed via mixed model for repeated

measures (MMRM) handle missing data via the maximum-likelihood function. The MMRM will be applied only when the number of subjects with non-missing values is more than 30% of the sample size. Following a hypothetical strategy estimand, non-PK data observed more than 7 days after the last dose of IP will not be used for the on-treatment related analysis visits. PK data observed more than 2 days after the last dose of IP will not be used for the on-treatment related analysis visits.

For analyses of binary endpoints, the non-responder imputation (NRI) method will be used for missing value imputation in addition to the observed case (OC) analysis.

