## Non-graded Abnormalities

The following worst-case post-baseline abnormalities L, N or H will be determined per subject, per laboratory test and for each analysis period, using all non-missing post-baseline records (including unscheduled and FU visits):

- L = low: at least one post-baseline result is classified as L.
- N = normal: all post-baseline results are classified as N.
- H = high: at least one post-baseline result is classified as H.

If, for a subject, both L and H are reported, the subject will be counted twice in the table: once with a worst-case L and once with a worst-case H.

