### 6.3.2.9. Presentation of Results

Continuous laboratory tests including, glucose, cholesterol, triglycerides, low-density lipoprotein (LDL), high-density lipoprotein (HDL) and fasted glucose, will be summarized by means of descriptive statistics (including 90% CI of the mean change) by laboratory test, treatment group and analysis window. Actual values and change from baseline will be tabulated separately.

Profile line plots by subject of all actual observed values using relative day (ADY) and profile plots on change from baseline by analysis window will be presented by treatment group. All values, including unscheduled visits will be presented in profile plot. If there are more than one visits on the same day, time will be considered to order them. Graphs of the mean (+ SE) actual values over time and the mean (+ SE) change from baseline, and percent changes from baseline will be presented for all continuous laboratory parameters, with the exception of the metabolic markers.

The analysis of abnormalities will focus on assessments reported during the treatment period. Results reported before baseline will only be listed.

Non-graded abnormalities and toxicities grades of the actual values will be presented as shift tables of the worst-case abnormality/toxicity grade versus the baseline abnormality/toxicity grade. The table will be created per laboratory test, treatment group and analysis window. The results of non-graded abnormalities and toxicities grades will be shown separately.

A frequency table of the number (percent) of subjects with treatment-emergent worst-case abnormalities/toxicity grade per laboratory test, treatment group and analysis period will be presented. The results of non-graded abnormalities and toxicities grades will be shown separately.

A frequency table of the number (percent) of subjects will be also provided for hepatotoxicity flags defined before. These abnormalities will be also flagged in the individual data laboratory listing.

Listing will be provided for the laboratory test along with flag for abnormality results. In addition, pregnancy result will be listed separately.

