#### Worst-Case Abnormality

The worst-case post-baseline categorized actual analysis value and the worst-case categorized change from baseline for QT and QTcF will be determined per subject, per parameter, and for each analysis period, using all non-missing post-baseline records (including unscheduled and FU visits).

The worst-case categorized actual analysis value is the category corresponding to the highest post-baseline actual value. In case of several equal highest post-baseline actual values, the earliest occurrence will be taken for the analyses and will be flagged in the listings.

The worst-case change from baseline is the category corresponding to the largest increase (positive change) from baseline. In case of several equal largest increase from baseline, the earliest occurrence will be taken for the analyses and will be flagged in the listings.

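### SAP 6.3.2.7: read where it stands, the closing sentence turns a subject's observed Grade 3-4 worst case into missing when one other laboratory record is missing

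*SAP*

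**What the plan says.** The toxicity-grading part of SAP 6.3.2.7 sets a worst-case grade for each subject, test, direction and analysis period, "using all non-missing post-baseline records (including unscheduled and FU visits"). The worst case is the highest grade. Five subject-level definitions follow, for Grade 0 to Grade 4. The closing sentence is: "If any record is missing, then the toxicity grade is considered as" missing. Nothing says which rule takes precedence or what counts as a missing record.

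Other parts of the SAP bear on this:

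- **4.4.1.2**, the general rule for missing results: "That is, an observed case (OC) analysis will be performed".
- **4.5.3**, percentages in worst-case analyses: "the denominator will be all subjects with (post-baseline) data for the parameter".
- **6.3.2.7, non-graded abnormalities**: a subject is high when "at least one post-baseline result is classified as H". There is no missing-record clause.
- **6.3.3.3, ECG**: "The worst-case categorized actual analysis value is the category corresponding to the highest post-baseline actual value". Vital signs (6.3.4.5) use the same definition. Neither has a missing-record clause.
- **6.3.2.9, outputs**: a frequency table gives the number and percent of "subjects with treatment-emergent worst-case abnormalities/toxicity grade per laboratory test, treatment group and analysis period will be presented". For the shift tables, "The table will be created per laboratory test, treatment group and analysis window".

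**The concern.** The two rules give different answers for a subject with an observed grade and one missing record in the same period. A worst-case summary should not lose an observed Grade 4 because another sample failed: whatever the missing result would have been, the worst case is already known to be at least Grade 4.

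If the closing sentence is programmed as written, that subject leaves the high-grade numerator of the treatment-emergent frequency table. The table matters more than usual here. The SAP introduction says the study was stopped for a liver safety signal and that only the primary endpoint and safety analyses will be produced.

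The CSR could also disagree with itself. SAP 6.3.2.6 defines treatment emergence on any post-baseline grade, and the note in Appendix I asks the CSR to describe treatment-emergent abnormalities of Grade 2 or above. The text could then describe a Grade 4 value that the frequency table counts as missing.

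**Working it through.** The plan gives no figure to reproduce, since this is a derivation rule and safety is descriptive (SAP 6.3). The check applies both rules to the same data.

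**1. One invented subject.** ALT grades at Weeks 1, 4, 8, 12 and follow-up: 0, 1, 4, no result, 0.
- Highest non-missing grade: max(0, 1, 4, 0) = Grade 4.
- Closing sentence as written: one record is missing, so the grade is missing.

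**2. Effect on the frequency table.** Planned arms are 20 and 10 (SAP 2.6). The subject has post-baseline data for the test, so on a plain reading of SAP 4.5.3 stays in the denominator.
- Change per relabelled subject: 1/20 = 5 points on GLPG3970; 1/10 = 10 points on placebo.
- Three Grade 3-4 cases on GLPG3970, one relabelled: 3/20 = 15% becomes 2/20 = 10%.
- A single case, relabelled: 1/20 = 5% becomes 0/20 = 0%.
- If subjects coded missing were instead dropped from the denominator, 3/20 would become 2/19 = 10.5%, and 1/20 would become 0/19 = 0%. The understatement remains, at a slightly different size.

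**3. How many records the clause looks across.** This depends on the test. In the schedule (SAP 2.5, Table 1), a completer has five post-baseline safety draws: Days 8, 29, 57, 85 and follow-up. Fasted glucose and fasted insulin are taken only at Visits 1, 4 and 5, which leaves two post-baseline results. For triglycerides, SAP 6.3.2.2 analyses fasted samples only, and Protocol 8.1 requires fasting only at Visits 1, 4 and 5.

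**4. Which missing records can trigger it.** SAP 4.3.2, Table 2, ends the Treatment period at the subject's last contact, so visits that would have fallen after a subject left are outside the period. What remains is a missing result while the subject is still in the study. Protocol 8 foresees assessments not done because of pandemic restrictions. Protocol 8.1.1 foresees hemolyzed, lost or destroyed samples, and allows one resample for such failures, including after screening. Neither document gives a rate.

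**5. Which outputs use the grade.** The frequency table is per analysis period, as the worst-case grade is, so it is directly exposed. The shift tables are laid out per analysis window, and the SAP does not say how a per-period worst case is shown by window, so an effect there is only possible.

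**The case against.** The strongest reply is that the sentence works at record level: no result, no grade. It says toxicity grade without the qualifier worst-case, and the list above it uses the plural of that term for individual records. It may also serve the shift tables, which need a missing category for an absent baseline or window result. Details of derivations are in a separate document (SAP 1) that may already do the sensible thing.

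Part of this stands. The sentence is ambiguous, and the documents do not show that the literal rule was programmed. But it closes a subject-level definition, says any rather than all, and at record level adds nothing for post-baseline records, which the opening sentence already limits to non-missing ones. Where the SAP means a missing attribute of a single event, as for AE severity in 6.3.1.5, it says so. A separate document does not cure a SAP rule that gives a wrong result when followed.

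Stronger readings are tempting but unsupported:

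- *The rule hides the liver signal.* It does not. The hepatotoxicity and possible Hy's Law tables (SAP 6.3.2.8) are defined on multiples of the upper limit of normal. The low/normal/high tables, listings and profile plots do not use the clause, and the CSR must still describe Grade 2 or higher abnormalities.
- *Early termination makes most subjects missing.* The Treatment period closes at last contact, so visits never reached need not count.
- *Every test needs five of five results.* The number differs by test, and an unheld visit may produce no record at all.
- *One arm is favoured.* No missingness rate, actual enrolment or imbalance is given.

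**Conclusion.** The point holds as a wording error in the SAP with a definite consequence if followed. The closing sentence conflicts with the opening rule of its own section and departs from the observed-case rule and the parallel worst-case definitions. Read where it stands, it understates the treatment-emergent worst-case toxicity frequency table, and possibly the shift tables.

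The size is 5 points per relabelled GLPG3970 subject and 10 per placebo subject, for the test concerned. This assumes the planned arms of 20 and 10 and that relabelled subjects stay in the denominator. How many subjects would be relabelled cannot be stated from the documents. Because the liver tables and the individual data are untouched, this should be fixed but does not threaten the study's main safety conclusion.

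**What to change.** Replace the closing sentence of the toxicity-grading part of SAP 6.3.2.7 with:

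*The worst-case grade is the highest grade among the available post-baseline records for that test, direction and analysis period; it is missing only if the subject has no non-missing post-baseline result for that test in that period.*

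Then confirm that the separate derivations document and the program follow it. The cost is one SAP sentence and a short check of the derivation. No new data are needed.
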